### **5.2.4 EANM procedure guidelines**

In the present study, we will calibrate and validate the EANM procedure guidelines for FDG-PET tumor imaging on a digital PET/CT system. Calibration of the required acquisition and reconstruction settings will be done by performing a phantom study. Afterwards, the digital PET/CT scans are reconstructed using the predefined acquisition and reconstruction settings.

For each patient, the conventional and digital PET/CT scans that fulfill EANM procedure guidelines will be visually compared by two NM physicians. For both datasets, they will provide a final diagnostic outcome which will be compared. These EANM-fulfilled scans will also be compared quantitatively, but we will be cautious to use those measurements for finite conclusions on EANM-validation due to the time delay between conventional and digital PET/CT.

### 5.3 Main study parameters

#### 5.3.1 Primary study parameter

##### Diagnostic outcome of the PET/CT study

*In more detail:*

- Number of lymph node metastasis
- Involved lymph node stations
- N-status
- Number of distant metastasis
- Involved distant metastatic systems (e.g. bone, brain, adrenals, liver, lungs)
- M-status
- Final TNM classification
- Sensitivity, specificity and accuracy for lymph node staging, distant metastatic and overall staging
- Unrelated accidental findings

#### 5.3.2 Secondary study parameter

##### PET image quality

*In more detail:*

- General PET image quality
  - Subjective: whole-body, liver and lung
  - Objective: liver and lung noise
- Diagnostic confidence for N- and M-staging
- Normal tissue appearance
- Lesion detectability (SUVmax, SUVmean (based on 50% SUVmax), lesion volume, lesion contrast, lesion contrast-to-noise ratio, lesion-to-liver ratio, lesion-to-aorta ratio as compared to lesion diameter measured on the attenuation CT)
- Optimal cut-off values of tumor uptake or lesion contrast to distinguish between benign and malignant lesions
- Optimal settings for digital PET to fulfill EANM procedure guidelines
- Comparison of conventional and digital PET fulfilling EANM procedure guidelines, based on:
  - Subjective opinion from NM physicians (lesion-based and patient-based)
  - Quantitative measurements (lesion-based)

#### **5.4 Withdrawal of individual subjects**

Subjects can leave the study at any time for any reason if they wish to do so without any consequences. The investigator can decide to withdraw a subject from the study for urgent medical reasons.

#### **5.5 Replacement of individual subjects after withdrawal**

If an included individual subject withdraws from the study, another subject can be included and replaces this subject.

#### **5.6 Follow-up of subjects withdrawn from treatment**

There will be no follow up of subjects, withdrawn from this study.

## **6. SAFETY REPORTING**

### **6.1 Section 10 WMO event**

In accordance to section 10, subsection 1, of the WMO, the investigator will inform the subjects and the reviewing accredited METC if anything occurs, on the basis of which it appears that the disadvantages of participation may be significantly greater than was foreseen in the research proposal. The study will be suspended pending further review by the accredited METC, except insofar as suspension would jeopardize the subjects' health. The investigator will take care that all subjects are kept informed.

### **6.2 AEs, SAEs and SUSARs**

#### **6.2.1 Adverse events (AEs)**

Adverse events are defined as any undesirable experience occurring to a subject during the study, whether or not considered related to the investigational product. All adverse events reported spontaneously by the subject or observed by the investigator or his staff will be recorded.

The occurrence of any adverse events due to the conduct of the study is not foreseen. Risks associated with the digital PET/CT system have been evaluated and are mitigated according to industry safety standards for radiation, mechanical, thermal, and electric hazards. Foreseeable adverse events associated with this investigation linked to the device would be considered very rare and would be the same type of physical events that could occur in any normal PET/CT scan. These would include pinching of skin, minor falls or bumps.

Normal risks of NM scans from the injection of a radiopharmaceutical include allergic reactions, swelling, infections, intravenous injuries, bruising, pain and discomfort. These hazards, if encountered, would likely occur as the result of the scheduled clinical PET/CT scan. Clinical guidelines for the PET and CT scan will be followed according to hospital policy.

The following adverse changes from baseline require reporting as Adverse Events:

- Any adverse change that has either of the following relations to the investigational device or study procedures: 'possibly related' or 'related'
- Any event that is an Unanticipated Adverse Device Effect

An adverse change that does not meet any of the above does not require reporting to the Sponsor (or the METC).

### **6.2.2 Serious adverse events (SAEs)**

A serious adverse event is any untoward medical occurrence or effect that at any dose:

- results in death;
- is life threatening (at the time of the event);
- requires hospitalization or prolongation of existing inpatients' hospitalization;
- results in persistent or significant disability or incapacity;
- is a congenital anomaly or birth defect;
- Any other important medical event that may not result in death, be life threatening, or require hospitalization, may be considered a serious adverse experience when, based upon appropriate medical judgment, the event may jeopardize the subject or may require an intervention to prevent one of the outcomes listed above.

The PI will report the SAEs through the web portal *ToetsingOnline* to the accredited METC that approved the protocol, within 15 days after the PI has first knowledge of the serious adverse events.

SAEs that result in death or are life threatening should be reported expedited. The expedited reporting will occur not later than 7 days after the responsible investigator has first knowledge of the adverse event. This is for a preliminary report with another 8 days for completion of the report.

### **6.3 Follow-up of adverse events**

All AEs will be followed until they have abated, or until a stable situation has been reached. Depending on the event, follow up may require additional tests or medical procedures as indicated, and/or referral to the general physician or a medical specialist.

SAEs need to be reported till end of study within the Netherlands, as defined in the protocol.

## 7. STATISTICAL ANALYSIS

### 7.1 Main study parameters

**Differences are specified as follows:** generally when performing the lesion-based or patient-based comparison between conventional and digital PET, all disagreements in measured scales, numbers of lesions and quantitative data will be regarded as differences. Furthermore, all disagreements in T, N and M stage between conventional and digital PET will be regarded as differences.

#### 7.1.1 Primary objective: diagnostic outcome of the PET/CT studies

For each patient separately, the diagnostic outcome for the conventional and digital PET/CT study will be compared. Measured ordinal differences in for example the N-status or the TNM classification will be assessed based on two methods. The first method is based on the sign test, in which the comparison results in an agreement or a disagreement. The second method is based on the Wilcoxon signed-ranked test, in which the amount of disagreement is also taken into account. Moreover, we will calculate agreement percentages on the diagnostic outcome between both systems. Furthermore, using validation results as a reference, we will determine the sensitivity, specificity and accuracy for both NM physicians based on the following formulas:

$$\text{Sensitivity} = N_{PET \text{ positive}} / N_{\text{true positive}}$$

$$\text{Specificity} = N_{PET \text{ negative}} / N_{\text{true negative}}$$

$$\text{Accuracy} = (N_{PET \text{ positive}} + N_{PET \text{ negative}}) / (N_{\text{true positive}} + N_{\text{true negative}})$$

To test whether differences in sensitivity, specificity and accuracy between conventional and digital PET/CT are significant, we will apply the McNemar paired proportion test. A p value of less than 0.05 will be considered to indicate statistical significance.

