## 2. OBJECTIVES

### 2.1 Primary objectives: lesion detection properties

*How does the diagnostic outcome of the digital PET/CT study compare to the outcome of conventional PET/CT in patients referred for (re)staging of lung cancer, breast cancer and esophageal cancer? In other words: does digital PET detect more, the same or less abnormalities in patients with cancer.*

*More in detail:*

- 1.1 What is the difference in the number of lymph node metastases?
- 1.2 What is the difference in the number of involved lymph node stations?
- 1.3 What is the difference in the N status?
- 1.4 What is the difference in the number of distant metastases?
- 1.5 What is the difference in the number of involved distant metastatic systems (e.g. bone, brain, adrenals, liver, lungs)?
- 1.6 What is the difference in the M status?
- 1.7 What is the overall difference in final TNM classification?
- 1.8 Using a composite reference standard, what is the sensitivity, specificity and accuracy for lymph node staging, distant metastatic and overall staging of digital PET/CT as compared to conventional PET/CT?
- 1.9 Is there a difference in unrelated accidental findings?

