### **3. STUDY DESIGN**

We will perform a single center diagnostic accuracy study, in which patient-scans obtained using two types of PET/CT scanners (1 clinical study on the conventional system and 1 clinical study on the digital system) will be intra-individually compared.

Patient selection will be performed at the NM department in Isala. Patient eligibility will be based on the information provided by the referring specialist on the requisition for the clinical FDG-PET/CT study.

Patients will be included during the inclusion period of 6-12 months. Patients that meet the inclusion criteria and have signed informed consent will undergo two PET/CT scans on both the conventional and the digital PET system, immediately after each other. The scan order will be randomized per week:

- Week 1: first scan on conventional PET/CT, second scan on digital PET/CT.
- Week 2: first scan on digital PET/CT, second scan on conventional PET/CT. Etc.

For each patient, we start with a separate analysis of conventional and digital PET/CT images. One investigator will evaluate the PET/CT images quantitatively while two NM physicians will give qualitative (visual) judgments. Afterwards, we compare conventional and digital findings for all patients.

PET/CT data will be analyzed based on three subgroups of patients with lung cancer, breast cancer and esophageal cancer respectively. Pathology results and follow-up imaging by PET, CT, echography and MRI will be used as gold standard. When validation results are not available, conventional and digital PET/CT results are just compared with each other. More information on data analysis is described in section 5.2.

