### **Optimal cut-off values**

To compare the performance of various quantitative PET evaluation parameters (such as lesion SUVmean, SUVmax and contrast), we will create receiver operating characteristic (ROC) curves and calculate sensitivity, specificity and accuracy values using validation results as a reference. Again, to test whether differences in sensitivity, specificity and accuracy between conventional and digital PET/CT are significant, we will apply the McNemar paired proportion test. A p value of less than 0.05 will be considered to indicate statistical significance. Finally, for each quantitative evaluation parameter, we will determine the optimal cut-off value to distinguish benign from malignant lesions on both conventional and digital PET/CT. This will be based on the value with optimal sensitivity and specificity (highest sum).

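### The formulas for sensitivity, specificity and accuracy in section 7.1.1 (primary objective 1.8) do not yield those measures, because their numerators count all PET-positive or PET-negative results, whether or not the reference agrees

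*Combined protocol and SAP*

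**What the plan says.** Objective 1.8 in section 2.1 asks, against a composite reference standard, "what is the sensitivity, specificity and accuracy for lymph node staging, distant metastatic and overall staging of digital PET/CT" in comparison with conventional PET/CT. Section 5.3.1 lists "Sensitivity, specificity and accuracy for lymph node staging, distant metastatic and overall staging" among the primary study parameters.

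The estimation rule is in section 7.1.1: "using validation results as a reference, we will determine the sensitivity, specificity and accuracy for both NM physicians based on the following formulas". Three ratios follow:

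- sensitivity: the number of PET positives over the number of 'true positives';
- specificity: the number of PET negatives over the number of 'true negatives';
- accuracy: the sum of the two numerators over the sum of the two denominators.

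Differences between scanners in all three measures are then tested with McNemar's test at p < 0.05. The cut-off analysis in section 7.1.2 will again "calculate sensitivity, specificity and accuracy values using validation results as a reference", without giving a formula. No section, including the list of abbreviations, defines the terms in the ratios.

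**The concern.** Sensitivity is the share of reference-positive units that the scan calls positive, so its numerator must be limited to reference-positive units. Specificity needs the same limit to reference-negative units, and accuracy must count only calls that agree with the reference. The formulas state none of these limits.

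Of the nine primary objectives in section 2.1, only 1.8 names a reference standard. Objectives 1.1 to 1.7 ask whether digital PET finds more or fewer lesions or changes the stage; they cannot show whether extra findings are real. If extra false positives can raise the reported sensitivity, the one primary analysis meant to separate better detection from over-calling no longer does so.

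**Working it through.** **Inputs.** The three formulas are from section 7.1.1. The plan gives no expected sensitivity, specificity or accuracy, so there is no figure to reproduce. The counts below are assumed and serve only as illustration; the algebra does not depend on them.

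**Notation.** TP, FP, FN and TN are the usual cells of PET result against reference, and N = TP+FP+FN+TN. PET positives are TP+FP and PET negatives are TN+FN. The correct measures are TP/(TP+FN), TN/(TN+FP) and (TP+TN)/N.

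**Reading 1: 'true' means reference status, verified units only.**

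- Sensitivity as written = (TP+FP)/(TP+FN) = 1 + (FP−FN)/(TP+FN)
- Specificity as written = (TN+FN)/(TN+FP) = 1 − (FP−FN)/(TN+FP)
- Accuracy as written = (TP+FP+TN+FN)/(TP+FN+TN+FP) = N/N = 1

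The first two depart from 100% only through the balance of false positives and false negatives. Unless FP = FN, exactly one of them exceeds 100%. Accuracy is 100% for every table, so it cannot differ between scanners.

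**Reading 2: 'true positive' and 'true negative' mean the TP and TN cells.**

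- Sensitivity as written = (TP+FP)/TP = 1/PPV
- Specificity as written = (TN+FN)/TN = 1/NPV
- Accuracy as written = N/(TP+TN) = 1/accuracy

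None can fall below 100%, and a less accurate scanner gets a higher 'accuracy'.

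**Assumed example, 50 diseased and 50 non-diseased units.** Scanner A: TP 30, FP 10, FN 20, TN 40. Scanner B: TP 36, FP 24, FN 14, TN 26.

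| | Sensitivity | Specificity | Accuracy |
|---|---|---|---|
| A, correct | 30/50 = 60% | 40/50 = 80% | 70/100 = 70% |
| B, correct | 36/50 = 72% | 26/50 = 52% | 62/100 = 62% |
| B − A, correct | +12 | −28 | −8 |
| A, reading 1 | 40/50 = 80% | 60/50 = 120% | 100/100 = 100% |
| B, reading 1 | 60/50 = 120% | 40/50 = 80% | 100/100 = 100% |
| B − A, reading 1 | +40 | −40 | 0 |
| A, reading 2 | 40/30 = 133.3% | 60/40 = 150% | 100/70 = 142.9% |
| B, reading 2 | 60/36 = 166.7% | 40/26 = 153.8% | 100/62 = 161.3% |
| B − A, reading 2 | +33.3 | +3.8 | +18.4 |

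**Extreme case on reading 1.** A perfect scanner (TP 50, FP 0, FN 0, TN 50) scores 100/100/100%. So does a coin toss (25 in each cell): 50/50, 50/50 and 100/100, where the correct values are 50/50/50%.

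**The case against.** The strongest reply is that this is a slip of notation and not a wrong analysis. The formulas carry standard names and follow a sentence that makes the validation results the reference. The next sentence applies a paired test of proportions to all three measures. Neither reading above fits that sentence: on reading 1 accuracy cannot differ between scanners, and on reading 2 the values are not proportions. What does fit is PET positive among reference positives and PET negative among reference negatives, which gives the standard measures. McNemar's test on paired correct/incorrect calls needs none of these formulas, and values above 100% would probably be noticed.

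Most of this stands as an account of what the authors meant. It does not repair the text, because the limiting condition is written nowhere. Detection is likely but not certain: an accuracy of exactly 100% does not look impossible, and when FP = FN all three values are 100% on reading 1. If the formulas were corrected only after results were seen, the numerators and denominators would become choices made after the fact.

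Two further limits are fair. Counting PET calls without a reference result would push reading 1 accuracy above 100%, but section 3 steers away from this: "When validation results are not available, conventional and digital PET/CT results are just compared with each other". The concern does not rest on it. And the cut-off analysis in section 7.1.2 does not refer back to these formulas, so it lacks a definition but is not shown to carry the error.

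**Conclusion.** The concern holds. As written, the three formulas do not give sensitivity, specificity or accuracy on either reading of their undefined terms; they become correct only if an unwritten condition is added to each numerator. On reading 1 the reported accuracy is fixed at 100% and the other two reflect only the balance of errors. On reading 2 the ordering of scanners by accuracy is reversed.

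That conclusion is algebraic and needs no assumption about the data. The sizes in the example (12 points shown as 40, 28 shown as 40, an 8-point loss hidden or shown as an 18.4-point gain) follow from the assumed counts and do not estimate bias in this trial. The damage is confined to the reported estimates for objective 1.8. The sample size rests on objectives 1.1 and 1.3 and is unaffected, as are the sign and Wilcoxon tests, and McNemar's test can still be run validly. Because the text misdefines a listed primary parameter, it should be corrected before the reference-based analysis is done.

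**What to change.** In section 7.1.1, define TP, FP, FN and TN against the composite reference and replace the formulas with:

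- sensitivity = TP/(TP+FN)
- specificity = TN/(TN+FP)
- accuracy = (TP+TN)/(all units with a reference result)

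State that these are calculated separately for each reader and each scanner. State the unit for each analysis, since section 7.1 leaves it open: "generally when performing the lesion-based or patient-based comparison between conventional and digital PET". Specify that McNemar's test compares paired correct/incorrect calls: in reference-positive units for sensitivity, in reference-negative units for specificity, and in all verified units for accuracy. Refer to the same definitions from the cut-off analysis in section 7.1.2.

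The cost is three formulas, a short paragraph of definitions and one cross-reference. No extra patients, scans or data are needed.

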#### 7.1.2 Secondary objective: PET image quality

##### General PET image quality

We will perform a population-based comparison between conventional and digital PET for general PET image quality and noise levels in the liver and lung. Differences in scores will be assessed using the sign test and the Wilcoxon signed-rank test. Furthermore, to evaluate the inter-observer variation between the subjective opinions from both NM physicians, we will calculate the kappa and compare the percentage agreement of PET image quality and noise levels in the liver and lung.

### **Diagnostic confidence**

Differences in diagnostic confidence between conventional and digital PET are assessed using the sign test and the Wilcoxon signed-rank test.

### **Normal tissue appearance**

When looking at the normal tissue appearance, we will perform a population-based comparison of average values in normal tissue uptake between conventional and digital PET/CT. Differences will be assessed using the Wilcoxon signed-rank test. It is expected that patient delay may influence normal tissue FDG-uptake. Therefore, we will study the presence of correlations between the amount of time-delay and differences in normal tissue uptake between conventional- and digital scans.

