#### 5.1.3 First PET/CT acquisition

Sixty minutes after FDG tracer injection, a standard clinical whole-body PET/CT scan is performed on the conventional or digital PET/CT scanner. (As mentioned in the study design, the PET scan order is randomized per week). For the first scan, the acquisition times are 1 and 2 minutes per bed position for patients with body weight up to 80 kilogram and from 81 kilogram respectively. To cover the whole-body region, on average 11 bed positions are required. This results in total PET

acquisition times of approximately 11 and 22 minutes for patients with body weight  $\leq 80$  kg and  $> 80$  kg respectively. Furthermore, attenuation CT acquisition takes around 5 minutes in all patients. Moreover, for many patients an additional diagnostic contrast-enhanced CT scan is acquired on the clinical PET/CT system with a total procedure time of approximately 15 minutes.

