#### **5.1.4 Second PET/CT acquisition (study procedure)**

Consecutively after the first PET/CT scan, an additional PET/CT scan is acquired on the second PET/CT system. To minimize the decrease in FDG present in the human body when performing the second PET/CT scan, the time between first and second PET/CT scan should be kept as short as possible. However, the amount of FDG present in the human body during the second PET/CT scan will be less as compared to the first PET/CT scan. Therefore, the acquisition time for second PET/CT scanning will equal to first PET/CT scan, plus a compensation for the radioactive decay. Due to differences in PET acquisition times and the acquisition of a diagnostic CT scan, there will be differences in delay time between patients. In general, patients can be divided in four groups for expected delay:

1. Patient bodyweight  $\leq 80$  kg and no diagnostic ceCT: delay  $\approx 21$  minutes
2. Patient bodyweight  $> 80$  kg and no diagnostic ceCT: delay  $\approx 32$  minutes
3. Patient bodyweight  $\leq 80$  kg and a diagnostic ceCT: delay  $\approx 36$  minutes
4. Patient bodyweight  $> 80$  kg and a diagnostic ceCT: delay  $\approx 47$  minutes

FDG has a half-life of 110 minutes. Using the formula for radioactive decay  $N(t) = N(0) \cdot 0.5^{T/T_{0.5}}$ , the percentage of FDG after the delay can be calculated. The correction factor is determined by calculating the inverse of the percentage of FDG, present after the delay. Based on this correction factor, the total acquisition time for the second PET/CT system can be calculated. Table 2 provides an indication of the scan times required for digital PET/CT scanning. As can be seen in this table, patients' bodyweight ( $\leq 80$  kg or  $> 80$  kg) is the main predicting factor whether the acquisition time on second PET takes approximately 20 minutes or approximately 35 minutes. Based on this estimation, we expect that the additional time for patients participating in this study will typically be 25 minutes but will not take more than 40 minutes.

**Table 2: Indications of total scan time on second PET/CT system, based on expected delays in four groups of patients.** The total scan time on second PET/CT includes the time for PET acquisition (with 11 bed positions (bp)) and attenuation CT acquisition.

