Patient group	Delay in minutes (≈)	Amount of FDG after delay (%)	Correction factor	Second PET, scan time per bp (s)	Second PET/CT scan time (min)
1	21	88%	1.14	60*1.14 = 68	18
2	32	82%	1.22	120*1.22 = 147	32
3	36	80%	1.25	60*1.25 = 75	19
4	47	74%	1.34	120*1.34 = 161	35

To provide an optimal comparison between conventional and digital PET/CT, we will use a patient-specific protocol for the second PET scan, based on the exact delay for each patient. This delay will be determined once the patient arrives in the room for the second PET/CT scan and will be used to set the final PET scan time per bed position for the second PET scan, for each patient separately.

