## 5.2 Data collection and analysis

### 5.2.1 General data collection

For each patient, we will collect several patient- and scan characteristics as presented in Figure 5.

Patient characteristics	
Date of birth	dd-mm-jjjj
Gender	Male/female
Diabetes	Yes / no / unknown
Length (cm)	.....
Weight (kg)	.....
Glucose (mmol/L)	.....
Directed by	Zwolle, Meppel, etcetera.
Indication	Staging / restaging / other / unknown

PET-scan parameters		CT-scan parameters	
PET/CT scanner	Ingenuity / Digital PET	mA	.....
Date of PET scan	dd-mm-jjjj	kV	.....
Time of FDG administration	.....	Idose	Yes / no
Start scan time	.....	CTDI (mGy)	.....
Netto activity (MBq)	.....	DLP (mGy * cm)	.....
Number of bed positions	.....		
Time per bed position (min)	.....		
PSF modulation	Yes / no		
Reconstruction voxel size	4 mm, 2 mm		

**Figure 5:** Description of patient- and scan characteristics that will be collected for this study.

For each patient, we will start with an analysis of both conventional and digital PET/CT images separately. One investigator will evaluate the PET/CT images quantitatively while two NM physicians will give qualitative (visual) judgments. When both conventional and digital PET/CT images from a patient are evaluated separately, the results will be compared and differences between the image datasets will be identified.

We will focus on PET/CT based TNM staging, which includes evaluation of the primary tumor, regional lymph nodes and distant metastasis. This means that for patients with (suspected) lung cancer, we will focus on the evaluation of primary lung tumor(s), mediastinal and hilar lymph nodes and distant metastases (in particular adrenal glands). For patient with (suspected) breast cancer, we will focus on the analysis of primary breast tumors, regional lymph nodes (axillary, subclaviculair, internal mammary and supraclavicular) and distant metastases. In patients suspicious for esophageal cancer, we will focus on the primary esophageal tumor, regional lymph nodes in the thorax and lower abdomen, and distant metastasis. Furthermore, other (rather unexpected) findings and differences between conventional and digital PET imaging will be studied and documented.

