## **5.2.2 PET/CT evaluation**

### **Quantitative evaluation**

The following general measurements will be performed on all PET images:

- Liver noise level
- Lung noise level
- Normal tissue uptake (SUVmean and SUVmax) in both lungs, blood pool, liver, both adrenal glands, spleen, bones and bone marrow.

For all lesions, the following measurements will be performed on PET images:

- SUVmax
- SUVmean (based on 50% SUVmax)
- Volume om mL (based on 50%SUVmax)
- Lesion contrast
- Lesion contrast-to-noise
- Lesion-to-liver ratio
- Lesion-to-aorta ratio

Furthermore, the lesion diameter as measured on the attenuation CT scan will be collected to make stratifications based on lesion diameter.

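### The planned delay correlation ignores which scanner came second, so on its natural reading a null result would not show that delay is unimportant

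*Combined protocol and SAP*

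**What the plan says.** The planned check is in section 7.1.2, Normal tissue appearance: "we will study the presence of correlations between the amount of time-delay and differences in normal tissue uptake between conventional- and digital scans". It follows a Wilcoxon signed-rank comparison of the two scanners and a statement that delay is expected to influence uptake. No coefficient, sign convention, order term or stratification is given.

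Three other parts of the protocol determine what this check can show.

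- **Scan order (section 3).** It alternates by week. Week 1 starts on the conventional scanner; then "Week 2: first scan on digital PET/CT, second scan on conventional PET/CT", and so on.
- **Delay (section 5.1.4).** It is the interval from first to second scan, about 21, 32, 36 or 47 minutes in four patient groups. "Due to differences in PET acquisition times and the acquisition of a diagnostic CT scan, there will be differences in delay time between patients". For each patient, "This delay will be determined once the patient arrives in the room for the second PET/CT scan".
- **Compensation (section 5.1.4).** "the acquisition time for second PET/CT scanning will equal to first PET/CT scan, plus a compensation for the radioactive decay". This lengthens the acquisition to offset decay. It does not address a change in tissue uptake between the scans.

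The scan-parameter form in section 5.2.1 records the scanner, the time of FDG administration and "Start scan time".

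**The concern.** A change in uptake between the first and second scan adds to the digital-minus-conventional difference when digital is second, and subtracts from it when digital is first. An unsigned delay does not distinguish the two cases. Pooled over both orders, the two halves pull in opposite directions and can leave no correlation even when delay matters a good deal. A null result could then be reported as reassurance that delay is unimportant, which it would not support. A positive result would also be hard to attribute to delay, because the length of the delay is set mainly by body weight and ceCT.

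**Working it through.** **Inputs from the protocol.** Delays of 21, 32, 36 and 47 min (section 5.1.4); half-life 110 min (same section); order alternating by week (section 3); 90, 90 and 45 patients, 225 in total (section 4.4). The protocol gives no size for a delay effect, so every effect size below is an assumption. Effects are in SDs of the within-patient difference, at the mean delay of (21+32+36+47)/4 = 34 min.

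**The protocol's own figures.** 0.5^(t/110) gives 87.6%, 81.7%, 79.7% and 74.4% of the FDG left, with factors 1.14, 1.22, 1.25 and 1.34. Table 2 is reproduced. The delays differ by 11 min (weight group) and 15 min (ceCT): 21+11 = 32, 21+15 = 36, 21+11+15 = 47. No figure is stated for the correlation itself.

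**Algebra.** Let d be digital minus conventional uptake, D the unsigned delay, and s = +1 if digital is second, −1 if first. Then

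d = scanner difference + s × b × D + error.

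If s is independent of D, Cov(D, d) = b × E(s) × Var(D). With 1:1 order E(s) = 0, so the covariance is zero for any b.

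**Simulation (n=90 / n=225, two-sided 0.05).** Half the patients are assumed to be above 80 kg and half to have a ceCT, independently of order.

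| Setting | Unsigned delay, signed difference |
|---|---|
| Delay effect 0.25, 0.5 or 1.0 SD | about 5% / 5% |
| No delay effect; scanner difference 0.5 SD larger above 80 kg | 17% / 37% |

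Modest imbalance restores little. At n=225 with a 1 SD delay effect, rejection is 8.5% at 55:45 and 12% at 60:40.

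**If ceCT adds delay only when the conventional scanner is first.** Delay now depends on order. Unsigned delay rejects in about 57% / 93% under a 0.5 SD delay effect, but also in about 51% / 87% under a pure 0.5 SD order effect with no delay effect. The result cannot separate the two. Mean delay would be 21+5.5+7.5 = 34 min in one order and 21+5.5 = 26.5 min in the other, so the average scanner comparison would keep 0.5 × (34−26.5)/34 = 0.11 of the delay effect, or 0.055 SD for a 0.5 SD effect.

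**Signed delay, no order term.** Rejection is 68% / 97% at 0.25 SD and over 99% at 0.5 SD. It is also 99% / 100% under a pure 0.5 SD order effect. The reason is arithmetic: Var(D) = (169+4+4+169)/4 = 86.5, so the correlation of s × D with s is 34/√(34²+86.5) = 34/35.25 = 0.96. This slope is a combined order and delay effect.

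**Order term added.** The standard error of the slope per 34 min is about 34/(9.3 × √n), which is 0.39 at n=90 and 0.24 at n=225. The 95% half-widths are therefore about 0.8 and 0.5 SD. Power is 25% / 52% at 0.5 SD and 72% / 98% at 1.0 SD, with 5% rejection under a pure order effect. But with no delay effect it rejects in about 27% / 59% if the first-to-second change is 0.5 SD larger above 80 kg, and 48% / 84% if it is 0.5 SD larger in ceCT patients.

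**The case against.** The text is under-specified rather than wrong. It does not exclude signing the delay, coding the difference as second minus first, or analysing each order separately, and the recorded start times allow all three. This stands. A reader might infer that the check cannot detect delay however it is run, but the wording does not go that far. The difficulty lies in the reading that the words most naturally suggest: delay as section 5.1.4 uses it, and a difference between scanners.

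Reading the differences as absolute is no reliable rescue. At 0.5 SD that version rejects in 10% / 18% at n=90 / n=225, and in 6% / 8% once the scanners differ by 1 SD.

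The cancellation also depends on how section 5.1.3 is read. It places the ceCT on the clinical system, which may mean whichever scanner is first or the conventional scanner. Under the second reading the expected correlation is no longer zero. This stands too, although the result is still not interpretable as a delay effect.

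Finally, adding an order term might be thought to isolate delay. It does not. Within an order, delay varies mainly through body weight and ceCT: by section 5.1.3, "the acquisition times are 1 and 2 minutes per bed position for patients with body weight up to 80 kilogram" and from 81 kg respectively, and the ceCT adds about 15 min.

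**Conclusion.** The concern holds for the natural reading: unsigned delay, signed difference, order about 1:1 and delay unrelated to order. The expected correlation is then zero whatever the delay effect, and this does not rest on the assumed effect sizes. If ceCT is tied to the conventional scanner, the correlation is not zero but mixes delay with order.

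The consequence is small. A reader might infer that the scanner comparison itself is biased or that false positives rise. With balanced order and delay unrelated to order, the average comparison is not biased. With a 0.5 SD delay effect the signed-rank type I error is about 3%, not inflated. No primary outcome depends on this check. It is worth correcting because the protocol itself expects a delay effect and the correction needs no new data.

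**What to change.** In section 7.1.2, Normal tissue appearance:

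1. Define delay as digital start time minus conventional start time, and regress the signed digital-minus-conventional difference on it. Keep the planned signed-rank tests.
2. Report the slope as a combined order and delay effect. Report the intercept as the scanner difference at equal time after injection, on the assumption that the effect is linear in delay.
3. As a sensitivity analysis, add a scan-order term and report the slope with its confidence interval. State that power is low (about 25% at n=90 and 52% at n=225 for an assumed 0.5 SD effect at 34 min). State also that the slope does not isolate delay, because delay within an order follows body weight and ceCT.
4. Say on which scanner the ceCT is acquired, so that readers can judge whether delay depends on order.

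Applying the same models to the lesion parameters is optional; it would need a patient random effect, because patients can have several lesions.

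The cost is a few sentences and slightly more analysis. With no delay effect the scanner comparison loses nothing (n=90, 0.3 SD scanner difference: 78% for signed-rank, 79% for the intercept). The order-adjusted slope may still not settle whether delay or another order effect is at work.
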